5.3.5. PF-04449913 in Combination with Azacitidine (Combination Cohort 3)

- Azacitidine will be administered SC or IV daily at a dose of 75 mg/m²/day on Days 1-7 of each 28-day cycle (After Cycle 1, ±3 days window applicable to each dose).
- PF-04449913 will be orally administered daily and continuously. In Cycle 1 only, administration of PF-04449913 will commence on Day 2 of the cycle (C1D2) to allow azacitidine alone PK sample collection. The starting dose will be 100 mg.

- Recommended dose modifications are discussed in Section 5.3.10.

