5.3.10. Recommended Dose Modifications [Combination Cohort 3 (Azacitidine Combination)]

Every effort should be made to administer the study drug treatment according to the planned dose and schedule. This section, package insert or institutional guideline for dose modification of azacitidine should be followed.

In the event of significant toxicity, dosing may be interrupted, delayed and/or reduced as outlined below. In the event of multiple toxicities, dose modification should be based on the worst toxicity observed. Patients must be instructed to notify investigators at the first occurrence of any adverse symptom/s.

Dose modifications may occur in three ways:

- **Within a cycle:** Dosing interruption until adequate recovery followed by dose reduction (if required) of PF-04449913 during a given treatment cycle. Azacitidine dosing interruption is not allowed within a cycle unless there is an unexpected or unacceptable study drug combination related toxicity or \geq Grade 3 non-hematologic toxicity.
- **Between cycles:** The next treatment cycle may be delayed if toxicity from the preceding cycle persists. If a treatment interruption continues beyond Day 28 of the current cycle for any agent, then the day when full treatment (all agents in the combination) is restarted will be counted as Day 1 of the next cycle for all agents.

- **In the next cycle:** Dose reduction may be required based on toxicities experienced in the previous cycle.

A study treatment related continuous treatment interruption or delay of >28 days (21 days in case of azacitidine related) for non-hematologic toxicity OR >42 days for prolonged myelosuppression defined as ANC <500/ μ L or platelet count <10 x10⁹/L in a normal bone marrow with <5% blasts and no evidence of disease or dysplasia, will result in permanent discontinuation from treatment, unless the patient is demonstrating clinical benefit as agreed by the Investigator and Sponsor (Table 18 and Table 19).

5.3.10.1. Dose Interruptions for Azacitidine and PF-04449913 [Combination Cohort 3 (Azacitidine Combination)]

Azacitidine

Azacitidine dose interruption is not allowed within a cycle unless there is an unacceptable or unexpected study drug combination related toxicity or \geq Grade 3 non-hematologic toxicity. In this case azacitidine dosing may be resumed following the dose modifications listed in Table 18 and Table 19.

After Cycle1, each dose of azacitidine will be allowed to be shifted by a plus or minus 3 day window.

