Patients experiencing \geq Grade 3 non-hematologic toxicities should have their azacitidine treatment interrupted regardless of when it occurs in the cycle until the toxicity returns to baseline. If the toxicity prolongs >21 days from when the next cycle is due to start or it becomes severe, azacitidine treatment will be discontinued permanently.

Appropriate follow up assessments should be implemented until adequate recovery occurs as assessed by the Investigator. The criteria that must be met prior to resuming treatment with azacitidine are outlined in Section 5.3.10.2.

Azacitidine administration should not be interrupted if PF-04449913 dosing is interrupted for toxicity.

PF-04449913

Patients experiencing \geq Grade 3 or persisting (at least 7 days not responding to optimal medical management) Grade 2 non-hematologic toxicities or myelosuppression defined as ANC <500/ μ L or platelet count <10 x10⁹/L in a normal bone marrow with <5% blasts and no evidence of disease or dysplasia potentially attributable to PF-04449913 should have their PF-04449913 treatment interrupted regardless of when it occurs in the cycle until the toxicity recovers to Grade 1 or less (for non-hematologic), Grade 2 or less (for hematologic) or baseline.

Appropriate follow-up assessments should be implemented until adequate recovery occurs. The criteria that must be met prior to resuming treatment with PF-04449913 are described in Section 5.3.10.2.

Depending on when the adverse event resolved, treatment interruption may lead to the patient missing all subsequent planned doses of PF-04449913 within the cycle. If the AE leading to treatment interruption recovers within the same cycle, re-commencement of dosing in that cycle is allowed. PF-04449913 doses omitted for toxicity will not be replaced within that cycle (eg, cycles will not be prolonged beyond the 28 days in order to make up for any missed PF-04449913 doses during that cycle).

The need for a dose reduction at the time of treatment resumption should be based on the criteria outlined in Section 5.3.10.3, unless specifically agreed otherwise following discussion between the Investigator and the Sponsor.

5.3.10.2. Dose Delays for Azacitidine and PF-04449913 [Combination Cohort 3 (Azacitidine Combination)]

Azacitidine

Hematologic toxicity is defined as below:

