\geq Grade 3 toxicity	Azacitidine should be interrupted regardless of when it occurs in the cycle. Azacitidine could be resumed when grade of the toxicity returns to baseline within 21 days from when the next cycle is due to start and ONLY if as per investigator judgment there will be a patient's clinical benefit to justify continuation of treatment	
Nausea, vomiting, or diarrhea must persist at \geq Grade 3 despite maximal appropriate medical therapy to require dose modification
 
In case of Grade 3; Withhold dose until toxicity is grade ≤ 1, or has returned to baseline, then resume treatment at the same dose level or reduce the dose by 1 level at the discretion of the investigator.
 
In case of Grade 4; Withhold dose until toxicity is grade ≤ 1, or has returned to baseline, then reduce the dose by 1 level and resume treatment, or discontinue at the discretion of the investigator.
 
Permanently discontinue if the continuous treatment interruption or delay of >28 days

5.3.11. Recommended Dose Modifications for PF-04449913 QTcF Prolongation and Drug Class Related AEs [Monotherapy Cohort, Combination Cohort 1 (Unfit Patients), Combination Cohort 2 (Fit Patients), Combination Cohort 3 (Azacitidine Combination)]

QTcF Interval Monitoring and Management: Patients should be closely monitored for potential cardiovascular symptoms. Appropriate monitoring should include clinical examinations, vital signs, routine ECGs, and AE monitoring. In case of QTc prolongation, concomitant conditions such as electrolyte imbalances, hypoxia, or use of medications affecting the QT interval should be ruled out or corrected. In case of clinically significant toxicities, PF-

04449913 administration should be interrupted and the dose reduced as indicated in [Table 20](#) (PF-04449913 Dose Modifications for mean QTcF (mQTcF) Prolongation).

Concomitant administration of PF-04449913 with moderate/strong CYP3A4/5 inhibitors ([Appendix 12](#)) is not permitted. And concomitant administration of PF-04449913 with drugs with known risk of Torsade de Pointes (TdP) ([Appendix 11](#)) is not recommended due to the potential for drug-drug interaction to prolong the QTc interval. However, if it is medically necessary for patients to use these medications please refer to Section [7.1.5](#) for details on required assessments and monitoring procedures (excluding the Expansion Cohort of LDAC combination for efficacy).

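### In Combination Cohort 3, one unqualified sentence keeps azacitidine going during a PF-04449913 hold, against the protocol's own rule for Grade 3 or higher non-hematologic toxicity

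*Protocol*

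**What the plan says.** Protocol Section 5.3.10 and its subsections set the dose modifications for the azacitidine combination.

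- **Permission to interrupt azacitidine.** Section 5.3.10 says: "Azacitidine dosing interruption is not allowed within a cycle unless there is an unexpected or unacceptable study drug combination related toxicity". The clause goes on to name Grade 3 or higher non-hematologic toxicity as a further exception. Section 5.3.10.1 opens with the same two exceptions.
- **Order to interrupt azacitidine.** Section 5.3.10.1 then says that patients with Grade 3 or higher non-hematologic toxicity "should have their azacitidine treatment interrupted regardless of when it occurs in the cycle until the toxicity returns to baseline".
- **The sentence at issue.** The azacitidine part of Section 5.3.10.1 closes with: "Azacitidine administration should not be interrupted if PF-04449913 dosing is interrupted for toxicity". It carries no grade, no attribution and no exception.
- **Order to interrupt PF-04449913.** The PF-04449913 part follows. Patients with Grade 3 or higher non-hematologic toxicity, persisting Grade 2 non-hematologic toxicity or a defined myelosuppression "potentially attributable to PF-04449913 should have their PF-04449913 treatment interrupted regardless of when it occurs in the cycle".
- **Table 19, Grade 3 or higher row.** The azacitidine column reads: "Azacitidine should be interrupted regardless of when it occurs in the cycle". The PF-04449913 column withholds that drug for the same event.
- **Dosing days.** Section 5.3.5 gives azacitidine "on Days 1-7 of each 28-day cycle" and starts PF-04449913 on Day 2 of Cycle 1. After Cycle 1, "each dose of azacitidine will be allowed to be shifted by a plus or minus 3 day window".

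**The concern.** A site handling a Grade 3 toxicity during the azacitidine week needs one answer to whether the next azacitidine dose is given. For an event that also stops PF-04449913, the protocol gives two. The sentence comes after the Grade 3 rule and ends the azacitidine subsection, so it can be read as overriding that rule, and nothing states which prevails.

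What is at stake is patient safety. Taken at its word, the sentence continues a cytotoxic drug through a Grade 3 or 4 non-hematologic toxicity. The situation is not confined to Cycle 1: Section 3.1.2 intends at least 6 cycles of the combination.

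**Working it through.** The plan gives no figure to reproduce here. The check sets the instructions side by side for each kind of event that can occur while azacitidine is being dosed.

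| Event on an azacitidine dosing day | PF-04449913 | Azacitidine, by its own rules | Azacitidine, by the closing sentence | Conflict? |
|---|---|---|---|---|
| Grade 3 or higher non-hematologic, potentially attributable to PF-04449913, within the Table 19 row, PF-04449913 held | Hold | Interrupt (Section 5.3.10.1 and Table 19) | Do not interrupt | Yes, with both |
| Grade 3 QTc prolongation, muscle spasm or myalgia, PF-04449913 held | Hold (Tables 20 and 21) | Interrupt under Section 5.3.10.1, which has no exclusion; the Table 19 row does not apply | Do not interrupt | Yes, with Section 5.3.10.1 only |
| Grade 3 or higher nausea, vomiting or diarrhea that responds to maximal therapy | No hold under Table 19 | Not needed for this check | Not triggered | No, under Table 19 |
| Grade 3 or higher non-hematologic, not attributable to PF-04449913, PF-04449913 not held | No hold | Interrupt | Not triggered | No |
| Persisting Grade 2 non-hematologic | Hold | No change (Table 19) | Do not interrupt | No |
| Defined myelosuppression | Hold | No within-cycle interruption required | Do not interrupt | No |

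For the first row the steps are:

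1. The PF-04449913 rule stops PF-04449913.
2. The azacitidine rule stops azacitidine.
3. Step 1 meets the condition of the closing sentence, which says not to stop azacitidine.

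Steps 2 and 3 cannot both be followed.

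**When it can happen.** Azacitidine has 7 nominal dosing days per 28-day cycle, and 7/28 = 25%. In Cycle 1 PF-04449913 starts on Day 2, so both drugs are given on Days 2-7, which is 6 days. In later cycles they share Days 1-7. With the 3-day shift, a later-cycle azacitidine dose can fall as late as Day 10 (7 + 3). Outside the dosing days there is no azacitidine dose to give or withhold, so the sentence has no effect.

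**The case against.** The best defence is that the text has a sensible reading. The subsection first lists when azacitidine may be interrupted, then makes interruption mandatory for Grade 3 or higher non-hematologic toxicity. In that position, the last sentence can mean only that holding PF-04449913 is not by itself a trigger for holding azacitidine. It has real work to do on that reading, because persisting Grade 2 toxicity and the defined myelosuppression hold PF-04449913 alone. Four statements favour it: Section 5.3.10, the opening of Section 5.3.10.1, the mandatory rule and Table 19. The modifications are titled as recommendations, and Section 5.3.10 directs sites to that section, the package insert or institutional guidance and says that the worst toxicity governs when there are several. Azacitidine is also given by site staff, who would have to act against an explicit table row.

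Most of this stands. It is the likely intent, and the documents do not show that any site continued azacitidine through such an event. But the sentence does not say it. No order of precedence is given, and the worst-toxicity rule does not settle opposite instructions about a single event. Pointing to other guidance does not say which of two protocol sentences governs. The neighbouring clauses state their exceptions explicitly; this one states none.

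A reader might also infer that the sentence distorts the Cycle 1 DLT count through criterion 3 of Section 3.2, the 80% dose-delivery rule. Two missed azacitidine doses leave 5 of 7 (71%), so the thought is natural. The documents do not support it as a finding. It needs four things at once:

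- The event is not already a DLT under criterion 1.
- Azacitidine doses are not made up. Section 5.3.10.1 bars replacement within the cycle for PF-04449913 but does not say so for azacitidine.
- Both drugs are held for equal lengths, although azacitidine waits for return to baseline while PF-04449913 may resume at Grade 1 or baseline.
- Criterion 3 is met when any one agent falls below 80%, not only when all do.

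**Conclusion.** The sentence is wrong as written and should be corrected as a matter of dosing safety. It contradicts Section 5.3.10.1 whenever a Grade 3 or higher non-hematologic event is potentially attributable to PF-04449913, leads to a PF-04449913 hold and overlaps azacitidine dosing. It contradicts Table 19 as well, except for QTc prolongation, muscle spasms and myalgia, which the row excludes, and for nausea, vomiting or diarrhea that responds to maximal therapy, which does not lead to a hold under that table.

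The scope is limited to one cohort of 6 patients and to azacitidine dosing days, but extends to any cycle. The conclusion rests only on reading the sentence as it stands; it assumes nothing about how often such events occur. Interrupting azacitidine is the better-supported instruction.

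The point does not reach the trial's statistics. SAP Section 4.1 sets no formal hypothesis for this cohort. An effect on DLT criterion 3 remains speculative and forms no part of the conclusion; under Section 3.1.2, 2 or more DLTs in 6 patients would lead to a safety review here, not an automatic dose change.

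**What to change.** Replace the closing sentence of the azacitidine part of Section 5.3.10.1 with:

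> Interruption of PF-04449913 for toxicity is not in itself a reason to interrupt azacitidine; azacitidine should be interrupted only if the toxicity also meets the azacitidine interruption criteria above and in Table 19 (Grade 3 or higher non-hematologic toxicity, or unacceptable or unexpected study drug combination related toxicity).

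This keeps the evident purpose for persisting Grade 2 toxicity and myelosuppression, and removes the conflict for Grade 3 or higher events. Naming Table 19 keeps its exclusions in view. Whether the Section 5.3.10.1 rule should carry the same exclusions is a separate clinical decision that the sponsor could settle at the same time.

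The cost is a one-sentence protocol clarification. Sample size, data collection and analysis do not change.

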- Patients without reduced baseline counts (defined as an absolute neutrophil count (ANC) $\geq 1,500/\mu\text{L}$, white blood cells $\geq 3,000/\mu\text{L}$ and platelets $\geq 75,000/\mu\text{L}$ prior to the first cycle):
 - Hematologic toxicity is defined as: the lowest count for the previous cycle showed ANC $< 1,000/\mu\text{L}$ or platelets $< 50,000/\mu\text{L}$.
- Patients with reduced baseline counts (defined as ANC $< 1,500/\mu\text{L}$, white blood cells $< 3,000/\mu\text{L}$ or platelets $< 75,000/\mu\text{L}$ prior to the first cycle):
 - Hematologic toxicity is defined as: any parameters of ANC, white blood cells or platelets decreases to 50% of baseline or below.

For each case, at the start of each new cycle, re-treatment with azacitidine may not occur until the **Neutrophil and Platelet Recovery Parameters** described below are met:

$$\text{Counts} \geq (\text{lowest count}) + [0.5 \times (\text{baseline count} - \text{lowest count})]$$

PF-04449913

PF-04449913 treatment should be interrupted for toxicities described in Section 5.3.10.1. Re-commencement of treatment with PF-04449913 may not occur until the recovery parameters described below are met:

- Hematologic toxicities have returned to baseline or \leq Grade 2 severity, provided that patients recovered from myelosuppression (defined as ANC $< 500/\mu\text{L}$ or

platelets $<10 \times 10^9/L$ in a normal bone marrow with $<5\%$ blasts and no evidence of disease or dysplasia) within 42 days and re-treatment can occur safely as per the Investigator's judgment.

- Non-hematologic toxicities have returned to baseline or \leq Grade 1 severity within ≤ 28 days of dose interruption or delay.

If these conditions are met, PF-04449913 may be resumed (see Section 5.3.10.3 for toxicities requiring dose reduction at the time of treatment resumption).

If myelosuppression (defined as ANC $<500/\mu L$ or platelets $<10 \times 10^9/L$ in a normal bone marrow with $<5\%$ blasts and no evidence of disease or dysplasia) prolongs for >42 days or non-hematologic toxicities need >28 days of dose interruption or delay, permanent discontinuation of treatment with PF-04449913 should be considered.

5.3.10.3. Dose Reductions for Azacitidine and PF-04449913 [Combination Cohort 3 (Azacitidine Combination)]

Following dosing interruption or cycle delay due to toxicity, the azacitidine and/or PF-04449913 dose may need to be reduced when treatment is resumed.

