Dose reduction of azacitidine and/or PF-04449913 by 1 or if necessary, 2 dose levels will be allowed depending on the type and severity of toxicity encountered (Table 17). Patients requiring more than 2 dose reductions of azacitidine should permanently discontinue both azacitidine and PF-04449913. **NOTE:** In the specific situations where clinical benefit is observed, PF-04449913 can be reduced below 50 mg QD upon Sponsor approval. All dose modifications/adjustments must be clearly documented in the CRF.

Once the PF-04449913 dose has been reduced, all subsequent cycles should be administered at that dose level, unless further dose reduction is required. Dose re-escalation is not allowed.

Once the azacitidine dose has been reduced for a given patient, subsequent cycles should be administered at that dose level. If dose re-escalation could be acceptable (ex. a patient undergoes two cycles at a reduced dose without recurrent hematologic toxicity), dose re-escalation to the next higher dose level could be considered following discussion and agreement between the Investigator and Sponsor.

Table 17 Available Dose Levels (Combination Cohort 3)

Azacitidine (mg/m ² /day)	PF-04449913 (mg QD)
75 (100%)	100
50% of current dose	75
33% of current dose	50
	25 *

* NOTE: If clinical benefit is observed, PF-04449913 may be reduced below 50 mg QD following Sponsor approval.

Recommended dose modifications for treatment-related hematologic toxicities are outlined in Table 18.

Table 18 Recommended Dose Modifications for Hematologic Toxicities

Toxicity	Azacitidine dose at Start of Subsequent Cycle	PF-04449913 ³ regardless of when it occurs in the cycle								
Hematologic toxicity ^{1,2} Recovery ⁴ within 14 days from when the next cycle is due to start (corresponding to recovery before or on Day 42 of the current cycle)	No change	-								
Hematologic toxicity ^{1,2} Recovery ⁴ after 14 days from when the next cycle is due to start (corresponding to recovery after Day 42 of the current cycle)	Without reduced baseline counts ¹ Decrease to 50% of the current dose	-								
	With reduced baseline counts ²									

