	
  
 Bone marrow cellularity	Dose in the Subsequent Cycle	
   
 >50%	No change	
 
 15%-50%	Decrease to 50% of the current dose if recovery⁴ after 21 days from when the next cycle is due to start	
 
 <15%	Decrease to 33% of the current dose if recovery⁴ after 21 days from when the next cycle is due to start	
  
		Bone marrow cellularity	Dose in the Subsequent Cycle	>50%	No change	15%-50%	Decrease to 50% of the current dose if recovery ⁴ after 21 days from when the next cycle is due to start	<15%	Decrease to 33% of the current dose if recovery ⁴ after 21 days from when the next cycle is due to start
	Bone marrow cellularity		Dose in the Subsequent Cycle							
>50%	No change									
15%-50%	Decrease to 50% of the current dose if recovery ⁴ after 21 days from when the next cycle is due to start									
<15%	Decrease to 33% of the current dose if recovery ⁴ after 21 days from when the next cycle is due to start									
Hematologic - ≤42 days prolongation of myelosuppression ⁵	-	Withhold dose until toxicity is grade ≤2, or has returned to baseline, then reduce the dose by 1 level and resume treatment, or discontinue at the discretion of the investigator.								
Hematologic - >42 days prolongation of myelosuppression ⁵	Permanently discontinue	Permanently discontinue								

1. For patients without reduced baseline counts (defined as ANC ≥1,500/μL, white blood cells ≥3,000/μL and platelets ≥75,000/μL prior to the first cycle): hematologic toxicity is defined as: ANC <1,000/μL or platelets <50,000/μL.

2. For patients with reduced baseline counts (defined as ANC <1,500/μL, white blood cells <3,000/μL or platelets <75,000/μL prior to the first cycle): hematologic toxicity is defined as: more than one parameter of ANC, white blood cells or platelets decreases to 50% of baseline or below.

3. PF-04449913 treatment should be interrupted for myelosuppression (defined as ANC <500/μL or platelet count <10 x10⁹/L in a normal bone marrow with <5% blasts and no evidence of disease or dysplasia) regardless of when it occurs.

4. Counts ≥(lowest count) + [0.5 × (baseline count – lowest count)]

5. Myelosuppression is defined as ANC <500/ μ L or platelet count <10 x10⁹/L in a normal bone marrow with <5% blasts and no evidence of disease or dysplasia

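### Combination Cohort 3, reduced baseline counts: one fallen count is azacitidine haematologic toxicity in Section 5.3.10.2 but not in Table 18 footnote 2, so the next dose has two readings in a narrow set of cases

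*Protocol*

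**What the plan says.** Both places describe the same patients: those in Combination Cohort 3 who, before the first cycle, had ANC below 1,500/µL, white cells below 3,000/µL or platelets below 75,000/µL.

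- **Protocol Section 5.3.10.2 (dose delays).** Haematologic toxicity means that "any parameters of ANC, white blood cells or platelets decreases to 50% of baseline or below". At the start of a new cycle, "re-treatment with azacitidine may not occur until the" recovery criterion is met. That criterion is labelled "Neutrophil and Platelet Recovery Parameters" and asks counts to regain at least half of the distance from their lowest value back to baseline.
- **Protocol Table 18, footnote 2.** Haematologic toxicity means that "more than one parameter of ANC, white blood cells or platelets decreases to 50% of baseline or below". The footnote is attached to the two haematologic-toxicity rows, and the azacitidine column of the table is headed "Azacitidine dose at Start of Subsequent Cycle".

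In those rows, recovery within 14 days of the due date of the next cycle means no dose change. If recovery is later than that, the entry for patients with reduced baseline counts goes by marrow cellularity:

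- above 50%: no change;
- 15% to 50%: "Decrease to 50% of the current dose if recovery" comes more than 21 days after the next cycle was due;
- below 15%: "Decrease to 33% of the current dose if recovery" comes more than 21 days after the next cycle was due.

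Section 5.3.10.3 introduces Table 18 as applying to treatment-related haematologic toxicity.

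**The concern.** The term, the population, the three counts and the 50% threshold are the same in both places. Only the number of counts that must fall differs. A patient in whom exactly one count falls is therefore delayed under the Section 5.3.10.2 definition, yet does not have haematologic toxicity under the footnote that governs the dose at restart.

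The rest of Table 18 follows Section 5.3.10.2. Footnote 4 repeats the recovery formula, and footnote 1 uses the same cut-offs for patients without reduced baseline counts (ANC 1,000/µL, platelets 50,000/µL). No sentence says that delay and dose reduction are meant to rest on different definitions.

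At stake is whether two sites, following the same protocol for the same patient, would restart a cytotoxic drug at the same dose. A smaller matter is the dose-reduction summary for azacitidine in SAP Section 8.2.10.1.4.

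**Working it through.** The plan states no figure on this point, so there is nothing to reproduce. The check asks where the two definitions disagree, and where that disagreement changes a dose.

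**1. Patterns of fallen counts.** Each of three counts is either above 50% of baseline, or at or below it: 2³ = 8 patterns.

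- At least one fallen: 8 − 1 = 7 patterns.
- More than one fallen: 3 pairs + 1 triple = 4 patterns.
- Disagreement: 7 − 4 = 3 patterns (ANC alone, white cells alone, platelets alone).

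These are logical cases, not probabilities. Neutrophils are part of the white count, so the patterns are not independent.

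**2. When a one-count fall changes the dose.** Table 18 equates 14 days late with Day 42 (28 + 14), so 21 days late is Day 49 (28 + 21). If the Section 5.3.10.2 definition is carried into Table 18, the azacitidine dose as a share of the current dose is:

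| Recovery after the next cycle was due | Cellularity >50% | 15–50% | <15% |
|---|---|---|---|
| up to 14 days | no change | no change | no change |
| over 14 to 21 days | no change | no reduction stated | no reduction stated |
| over 21 days | no change | 50% | 33% |

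Under footnote 2 no haematologic-toxicity row applies in any of the nine cells. The readings therefore give different doses in 2 of 9 cells.

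**3. Conditions that must hold together.**

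- The toxicity is treatment-related.
- Baseline counts are reduced.
- Exactly one count is at or below 50% of baseline.
- Recovery comes more than 21 days after the next cycle was due.
- Marrow cellularity is 50% or less.
- The myelosuppression rows do not apply. Footnote 5 defines these by ANC below 500/µL or platelets below 10 × 10⁹/L in a normal marrow, so ANC of at least 500/µL with platelets of at least 10 × 10⁹/L is enough to rule them out.

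**4. Worked example (counts assumed).** Baseline: ANC 1,200, white cells 2,800, platelets 60,000/µL. Lowest: 800, 1,900 and 28,000/µL.

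- Ratios: 800/1,200 = 67%; 1,900/2,800 = 68%; 28,000/60,000 = 47%. Only platelets are at or below 50%.
- Section 5.3.10.2 is met; footnote 2 is not.
- Restart thresholds: platelets 28,000 + 0.5 × (60,000 − 28,000) = 44,000/µL; ANC 800 + 0.5 × (1,200 − 800) = 1,000/µL.
- ANC of 800/µL and platelets of 28,000/µL are both above the footnote 5 limits, so the myelosuppression rows do not apply.
- Suppose that ANC recovers in time but platelets reach 44,000/µL only after Day 49, and that the toxicity is treatment-related. From the 75 mg/m²/day in Section 5.3.5, the Section 5.3.10.2 definition leads to 0.50 × 75 = 37.5 mg/m²/day (cellularity 15–50%) or 0.33 × 75 = 24.75 mg/m²/day (below 15%). Footnote 2 leads to no haematologic-toxicity row.

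**5. Effect on the SAP table.** SAP Section 8.2.10.1.4 counts each subject once if there is any day on which the dose taken was above zero but below the initial planned dose, for any reason. With 6 patients (Protocol Section 3.1.2), one affected patient changes that count by at most 1 of 6 (16.7 percentage points). The change is 0 if the patient has an azacitidine reduction for another reason, such as the renal or bicarbonate rules in Table 19.

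**The case against.** The best reply is that each definition sits beside its own consequence: Section 5.3.10.2 governs delay and footnote 2 governs dose. Read literally, a one-count fall delays restart and triggers no haematologic-toxicity reduction. A lower bar for delaying than for reducing is coherent. This stands as a possible reading. What it lacks is any sentence in the protocol saying that it is the intended one, and a site that applies the Section 5.3.10.2 definition throughout is equally faithful to the text.

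Two further replies carry less weight. Table 18 is headed as a recommendation, and Section 5.3.10 allows the package insert or institutional guideline to be followed; neither says which protocol definition applies. The wording in Section 5.3.10.2 is loosely plural, but its ordinary sense is at least one, and it does not ask for two.

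Some stronger readings are tempting. A reader might infer that restart timing is ambiguous as well. It is not, unless a site carries footnote 2 back into Section 5.3.10.2, which has its own definition. Nor does the sentence in Section 5.3.10.1 saying that "The criteria that must be met prior to resuming treatment with azacitidine are outlined in Section 5.3.10.2" add much: it follows text on interruption for non-haematologic toxicity. A reader might also infer that every affected patient moves the dose-reduction rate by a full sixth. The SAP counts subjects once and for any reason, so a sixth is the ceiling.

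**Conclusion.** The contradiction is real and should be corrected, but its reach is narrow. For reduced-baseline patients in Combination Cohort 3, the two definitions disagree whenever exactly one count is at or below 50% of baseline. The next azacitidine dose depends on the reading only when all the conditions in step 3 of the working hold together. In that case the choice is between 50% or 33% of the current dose and no applicable haematologic-toxicity row.

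The documents do not show how many of the 6 patients, if any, would meet those conditions, and no frequency is claimed. The example rests on assumed counts.

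A reader might infer that the cohort's tolerability decision or the study's formal efficacy test is exposed. The documents do not support that. Protocol Section 3.2 defines haematologic DLTs by its own criterion of prolonged myelosuppression and uses neither definition. The Expansion Cohort DMR test concerns other patients, who do not receive azacitidine.

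**What to change.** Reconcile Section 5.3.10.2 and Table 18 footnote 2 so that both carry one definition. Alternatively, state explicitly that delay and dose reduction use different definitions, and say what then applies to azacitidine after a one-count fall. Notify sites with patients still on azacitidine. Which rule is clinically right is for the sponsor and investigators; none is proposed here.

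The cost is a short clarification by letter or amendment, plus the site notice. It needs no new data collection and no SAP change.
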